In our own experience at Emory¹⁹ with 47 patients receiving HR for both solid intact metastasis (22) and resection cavities (25), we have demonstrated 6 month and 1 year LC rates of 69% (CI 0.62-0.77) and 59% (CI 0.67 – 0.50), with 3 (6.4%) patients experiencing symptomatic radiation necrosis. On multivariate Cox-regression analysis, improved local control was associated with smaller planned target volume (PTV) volume (SS, $p=0.02$) and higher dose per fraction (NS, $p=0.06$). No significant association was found between LC and previous RT received, resection cavity vs. solid tumor, total dose, biological equivalent dose (BED) or single fraction equivalent dose (SFED). These results show HR is well tolerated in both new and recurrent, previously irradiated large intact or resected brain metastases. Significantly higher rates of local failure are observed with larger PTV volumes suggesting a need for dose escalation when using HR for large intracranial lesions.

We propose a prospective phase I trial for patients with solid brain metastasis greater than 3cm and less than 6 cm, who have either had no treatment or who are status post surgical resection. The purpose of this trial will be to determine the maximum tolerated dose for fractionated radiosurgery delivered in 5 fractions with a minimum of 2 and a maximum of 3 fractions being delivered per week. Results from this trial may form the basis of future trials evaluating the efficacy of fractionated radiosurgery regimens for local and distant control of brain metastasis and for directly comparing WBRT with FRS, for patients not amenable to single fraction SRS. Such a phase III study would answer the question about as to whether local irradiation is adequate treatment for patients with large brain metastasis.

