3.3 Therapeutic and Diagnostic Procedures

All simulation and treatment procedures represent current institutional practice and will be the same for all study participants in each dose level

- 3.3.1** Radiation Therapy will consist of partial brain irradiation delivered to the metastatic brain tumor or resection cavity, delivered in 5 treatments with 2-3 treatments delivered per week.
- 3.3.2** CT Simulation will be performed for radiation therapy treatment planning purposes several days prior to the initiation of radiation therapy. This procedure consists of a CT scan performed in the treatment position. It is not for diagnostic purposes and is not itself therapeutic, but the CT image is required for radiation planning and delivery. This procedure is standard of care prior to therapeutic radiation.
- 3.3.3** Pre-treatment and post-treatment MRI of the brain. The patient will be required to undergo diagnostic MRI before and after radiation treatment as well as a treatment planning MRI. MRI will be ordered with and without gadolinium. This diagnostic procedure is standard of care for follow-up of intracranial metastases.

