3.8.1 Neurologic Toxicity Assessment

1. Neurologic/CNS Toxicity will be graded according to the Common Toxicity Criteria for Adverse Events (CTCAE) version 4.03 (**Appendix B**).
2. Toxicity assessment will be made during treatment at weekly MD visits and at each follow up (1 month and 4 months after completion of radiation therapy, and every 3 months thereafter). A plus or minus 3 week window will be allowed for follow-up assessments.
3. Toxicity will be classified as immediate (within 24 hours of treatment), acute (within 4 months), or chronic (more than 4 months) based on timing after SRS.
4. Toxicities of any grade should be recorded by the radiation oncology staff on the study specific case report form at the prespecified assessment time points. All \geq grade 3 nervous system toxicity will be reported to the study principle investigator (PI).
5. Toxicities attributed to chemotherapy recorded by medical oncology staff will not be captured as study related AEs.
6. Attribution will initially be scored by the study investigators on the case report form and/or the physician seeing the patient in follow-up visit on a five point scale: 5=definitely caused by radiation treatment, 4= probably caused by radiation treatment, 3=possibly caused by radiation treatment, 2= probably not caused by radiation treatment, 1= not due to radiation treatment. Attribution will be reviewed by the PI and co-investigators. Any \geq grade 3 CNS toxicity with attribution ≥ 3 will be considered at DLT and will be reported to the DSMC. If a grade 3 CNS toxicity occurs after the patients is considered off study this will not be considered a DLT.
7. Any grade 5 toxicity will halt the study for review by the DSMC and IRB.
8. Maximal Tolerated Dose (MTD)
The MTD will be defined as the highest dose level where a grade 3 or greater with an attribution score of ≥ 3 develops in ≤ 2 of 6 patients in a dose group within 4 months of the treatment.
9. Laboratory values are not required for this protocol and will not be collected.

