3.8.2 Imaging, Treatment Response and Tumor Control Assessment

Patients will undergo brain MRI prior to study entry and at 1 month, 4 months and every 3 months thereafter or when otherwise indicated (eg. at onset of clinical deterioration). A plus or minus 3 week window will be allowed for follow-up imaging and tumor response assessments.

1. Brain metastasis evaluation

The appearance (yes/no) of any new brain metastases will be recorded on all follow-up forms. Any new lesions on follow-up imaging will be defined as progression. Progression will be categorized as described below.

2. Primary Tumor or Resection Cavity response evaluation.

For intact solid tumors, the treated lesion will be evaluated on each follow-up MRI for evidence of progression and response according to the Response Evaluation Criteria for Solid Tumors (RECIST)(**Appendix C**). For resection cavities, residual disease or any new/progressive disease will also be measured. If there is no residual disease or progressive disease, the cavity will be considered stable and no measurements will be taken. New appearance of, or increase in, contrast enhancement of the cavity or surrounding vasogenic edema will be recorded.

3. Any situation where it is unclear whether the imaging changes are due to tumor relapse/progression versus radiation necrosis will require further work-up. This may include MR spectroscopy, MR perfusion, brain PET scan, or a combination of several modalities. In cases in which the patient is symptomatic and an unequivocal diagnosis cannot be made may require surgical intervention

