5.3 Statistical Analysis

5.3.1 Primary Analysis: The rate of toxicities at 4 months will be calculated with 95% confidence interval (CI).

5.3.2 Secondary Analysis:

5.3.2.1 The median time to local/distant brain progression will be calculated by Kaplan-Meier method with 95% CI. For a given time point, say 4 month, the rate of local/distant progression will be calculated with 95%CI.

5.3.2.2 The median of OS time with 95% CI will be calculated by Kaplan-Meier method.

5.3.2.3 Neurocognitive effect and QOL outcomes will be regressed over time using GEE model. The population change over time (slope) will be estimated with 95%CI.

5.3.3 Patient Stratification: All enrolled patients will proceed through dose escalation as a single cohort, however patients will be analyzed as separate strata, should enrollment allow it, based on the following criteria.

5.3.3.1 Intact brain metastasis versus resection cavity.

5.3.3.2 No previous cranial irradiation versus previous WBRT or other cranial irradiation.

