APPENDIX A – Patient Assessment Timeline

	Baseline	Weekly on RT	1 month	4 months	7 months	10 months	13 months	16 months	19 months	22 months	25 months
H&P	X		X	X	X	X	X	X	X	X	X
Toxicity Assessment		X	X	X	X	X	X	X	X	X	X
MRI	X		X	X	X	X	X	X	X	X	X
HVLT-R	X		X	X	X		X		X		X
MMSE	X		X	X	X		X		X		X
MOS	X		X	X	X		X		X		X
FACT-Br	X		X	X	X		X		X		X
Imaging Response Evaluation			X	X	X	X	X	X	X	X	X

*Assessments may occur within a +/- 3 week window the specified time.

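### A progression rate read at exactly 4 months falls in the middle of the 4-month MRI window and, with no dating rule in the plan, can be biased low

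*Combined protocol and SAP*

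**What the plan says.** Section 5.3.2.1 specifies Kaplan-Meier for the median: "The median time to local/distant brain progression will be calculated by Kaplan-Meier method with 95% CI". The next sentence adds the rate: "For a given time point, say 4 month, the rate of local/distant progression will be calculated with 95%CI". No other time point is named for it.

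Section 3.8.2 schedules brain MRI before study entry and then "at 1 month, 4 months and every 3 months thereafter or when otherwise indicated (eg. at onset of clinical deterioration"), and adds: "A plus or minus 3 week window will be allowed for follow-up imaging and tumor response assessments". Appendix A repeats the allowance for all assessments: "Assessments may occur within a +/- 3 week window the specified time".

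For toxicity visits, section 3.8.1 counts follow-up as "1 month and 4 months after completion of radiation therapy, and every 3 months thereafter". No origin is stated for time to progression. The documents also give no rule for dating progression (scan date, nominal visit or midpoint), no interval-censored method, and no rule for a 4-month scan done after 4.0 months.

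The Introduction reports the centre's own series: "we have demonstrated 6 month and 1 year LC rates of 69% (CI 0.62-0.77) and 59% (CI 0.67 – 0.50"). The other local control rates it gives for hypofractionated treatment, 68% and 80%, are also at 6 months.

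**The concern.** A progression that arises between the 1-month and 4-month scans is normally found at the 4-month scan. Under ordinary scan-date dating, the Kaplan-Meier step falls on the day of that scan. Take two patients with the same disease course, one scanned a week before 4.0 months and the other a week after. Both are within protocol, yet at 4.0 months the first counts as progressed and the second as progression-free.

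The error runs one way. Late imaging can only push an event past the cut-off, so the rate is understated and control overstated, and the planned confidence interval does not reflect this. Section 1.0 argues for dose escalation from local failure and expects the results to inform later efficacy trials, so a flattering early control figure could be carried forward.

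**Working it through.** The documents state no 4-month progression rate, so there is no figure to reproduce. The size has to be modelled.

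**Inputs**
- Window (section 3.8.2): w = 21/30.4375 = 0.69 month. The 1-month scan falls at 0.31 to 1.69 months and the 4-month scan at 3.31 to 4.69.
- Local control (section 1.0): 69% at 6 months and 59% at 1 year. No distant-brain rate is given, so only local progression can be sized.
- Assumed: scans uniform over the window, detection only at scheduled scans, dating by scan, clock from completion of radiation.

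**Formula.** Let F(t) be true progression by time t. Half of the 4-month scans fall by 4.0 months and reveal progression up to the scan; for the other half, only the 1-month scan counts. So

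counted(4.0) = ½ × mean of F over 3.31–4.00 + ½ × mean of F over 0.31–1.69

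share dated late = 1 − counted(4.0)/F(4)

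**Constant hazard through 69% at 6 months.** λ = −ln(0.69)/6 = 0.0618 per month and F(4) = 1 − exp(−4λ) = 21.9%. The two means are 20.2% and 6.0%, so counted = 13.1%. Share dated late = 40.2%; gap 8.8 points (5.3 against 3.1 of 24 patients).

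**Weibull through both control rates.** F(t) = 1 − exp(−b·t^k), with k = ln[ln 0.59/ln 0.69]/ln 2 = 0.508 and b = −ln(0.69)/6^k = 0.149. F(4) = 26.1%. The two means are 25.0% and 13.5%, so counted = 19.3%. Share dated late = 26.0%; gap 6.8 points (6.3 against 4.6 of 24).

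**Sensitivity of the late-dated share, by simulation of the same model**

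| Change | Constant hazard | Weibull |
|---|---|---|
| 25% of progressions found at onset by unscheduled MRI | 30.1% | 19.4% |
| 50% found at onset | 20.1% | 13.0% |
| Scans skewed early in the window | 26.1% | 16.8% |
| Scans skewed late | 51.3% | 32.0% |
| Clock from start of radiation, course of 10–21 days (assumed) | 48.4–54.9% | 30.0–32.4% |

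The course length is an assumption because section 3.3.1 says only that treatment is "delivered in 5 treatments with 2-3 treatments delivered per week". A rising hazard (Weibull shape 1.5 through 69% at 6 months) gives 48.7%, or 62.7% with late-skewed scans. If every scan fell at exactly 4.0 months, the share would be zero.

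**Reading at window close (4 months + 3 weeks).** Counted = mean of F over 3.31–4.69 = 21.9% (constant hazard) or 26.0% (Weibull), against true 4-month rates of 21.9% and 26.1%. The share of progressions by 4.0 months still dated late falls to 3.9% or 2.0%.

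**Reading at 6.0 months.** No scheduled scan falls between 4.69 and 6.31 months, so the count is still 21.9% or 26.0%, while true progression is 31.0% in both models. The shortfall is 9.1 or 5.0 points.

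**The case against.** **The text does not fix the biased reading.** The Kaplan-Meier sentence concerns the median; the rate sentence names no estimator, and 4 months is introduced as an example. In this protocol 4 months is also a visit, so the rate may mean the proportion progressed at that assessment, in which case the bias largely disappears. This softens the point, but the sentence follows directly on Kaplan-Meier and allows either reading. If 4 months is only an example, the time point is not pre-specified, and the same edit is needed.

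**The effect is small beside the noise.** At a 21.9% rate with 24 patients, the 95% half-width is 1.96 × √(0.219 × 0.781/24) = 16.6 points, against a bias of about 7 to 9. No test, threshold or escalation decision rests on this rate. That stands and limits the weight of the point. The bias is nevertheless systematic and costs nothing to remove.

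**Some detection is off schedule.** Section 3.8.2 allows MRI on clinical deterioration, and section 3.8.4 counts secondary treatment as local failure. Both reduce the late-dated share.

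**Stronger readings to avoid.** A reader might take 40% as the established loss. It needs a constant hazard, which implies 0.69² = 47.6% control at 1 year against the 59% in section 1.0. A reader might also call the centre of a window the worst place to read the curve. That is false: under constant hazard, a reading at 3.3 months, as the window opens, counts 6.0% against a true 18.5%. Nor does the plan rule out comparison with the 6-month series, since an example time point excludes nothing.

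**Conclusion.** The point holds in a conditional form. If progression is dated by scan and the curve is read at exactly 4.0 months, the local progression rate is biased low. About 26% (Weibull through both of the centre's control rates) to 40% (constant hazard) of progressions by 4 months are dated after the cut-off, a shortfall of about 7 to 9 percentage points. This rests on scans uniform over the window, detection only at scheduled MRI and a clock from completion of radiation. Other assumptions tested gave 13% to 55%, or 63% with a rising hazard and late scans. The background control rates were presumably found at scans too, so neither curve is the truth, and nothing in the documents allows distant progression to be sized.

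A reader might infer that these progressions are missed. They are not: they enter the curve later, at the delayed 4-month scan and mostly within 3 weeks after 4 months. The endpoint is secondary and descriptive, so the correction is worthwhile but does not affect dose finding.

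**What to change.** In section 5.3.2.1, state the time origin and how progression is dated. Then do one of the following:
- report the rate at the close of the 4-month and 7-month windows (nominal date plus 3 weeks, on the same clock), described as progression detected by that assessment;
- assign each scan to its nominal visit month; or
- use an interval-censored estimate.

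A 6-month estimate may be added for comparison with the background series, but it should be labelled as progression detected through the 4-month scan. Lying outside every window does not make it unbiased: it shows about 22% against a true 31% under constant hazard, or 26% against 31% under the Weibull.

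The cost is one sentence, with no new data or visits, and a slightly less favourable early progression rate.

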Stereotactic Radiosurgery, as defined by the American Society for Therapeutic Radiology and Oncology (ASTRO), the American Association of Neurological Surgeons (AANS), and the Congress of Neurological Surgeons (CNS), includes single dose SRS and well as HR delivered in 2-5 fractions over multiple days¹⁴⁻¹⁵. The majority of data supporting the use of SRS for the treatment of brain metastases has evaluated only single dose SRS and it is unclear whether the same results can be attributed to HR in 2-5 fractions. Brain metastasis amenable to single fraction SRS are typically defined as those measuring less than 3cm and producing less than 1cm of midline shift³. For brain metastasis not amenable to SRS, but for which focal brain radiation is indicated for boost or as salvage after WBRT or for avoidance of neurocognitive decline, HR provides an alternative treatment option. Current data describing the use and results of HR for the treatment of brain metastasis is limited to few retrospective series. Pater and colleagues from University of Cincinnati have demonstrated HR delivered to a dose of 30 Gy in 5 fractions to be effective and tolerable in a series of 34 patients, with a 6% (n=2) incidence of asymptomatic radiation necrosis and a 6 month actuarial local control rate of 68%¹⁶. A second series of 43 patients with metastatic breast cancer treated at Staten Island University Hospital utilized HR to a dose of 24 Gy delivered in 4 fractions, with a median survival from treatment of 7.5 months¹⁷. Recently, Wang et al. have reported on the use of HR in the setting of resected brain metastasis with resection cavities > 3cm and have demonstrated a local control rate of 80% at 6 months with the use of 24 Gy in 3 daily fraction¹⁸. With only a few series reported, the optimal dose and fractionation schedule is unknown.

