2.2.1 Local control: lack of progression of disease in resection cavity

2.2.2 Distant control: lack of progression of disease in surrounding brain

2.2.3 Overall survival: death from any cause

2.2.4 Long-term neurocognitive outcomes: using the Hopkins Verbal Learning Test–Revised (HVLT-R), Mini Mental Status Exam (MMSE) and Cognitive Functioning Subscale of the Medical Outcomes Scale (MOS).

2.2.5 Quality of life (QOL) outcomes: using the quality of life questionnaire for the Functional Assessment of Cancer Therapy-Brain (FACT-Br).

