3.8.3 Neurocognitive/Quality of Life Outcome Assessments

All tests will be given at baseline (if the patient consents to completing them) and at every follow-up for the first 7 months, then every 6 months thereafter (at 1, 4, 7, 13, 19, and 25 months).

1. Tests to be administered:

Cognitive Domain	Assessment
Memory	Hopkins Verbal Learning Test-Revised
Global Function	Mini-Mental Status Examination
Cognitive Function (self-report)	Medical Outcomes Cognitive Scale
Quality of Life	Functional Assessment of Cancer Therapy-Brain (FACT-Br)

2. Hopkins Verbal Learning Test- Revised (HVLT-R)

The patient learns 12 words read to them 3 times; free recall is tested after each learning trial. Delayed recall is evaluated after 20 minutes. Following the delayed recall trial, the patient completes a delayed recognition test to determine if an impairment of delayed recall is due to a retrieval deficit or to a consolidation deficit. Entire test requires about 5 minutes to complete, excluding waiting period before delayed recall.

3. Mini-Mental Status Examination (MMSE)

This is a brief, standardized tool to grade patients' global cognitive function. The MMSE begins with an assessment of orientation to place and time. Next is a test of memory (immediate recall) by having the subject immediately repeat the names of 3 objects presented orally. Following this, the patient subtracts sevens serially from 100. The subject is then asked to recall the three items previously repeated (delayed recall). The final section evaluates aphasia and apraxia by testing naming, repetition, compliance with a 3-step command, comprehension of written words, writing, and copying a drawing. The maximum score that can be obtained for the entire MMSE is 30 points.

4. Cognitive Functioning Subscale of the Medical Outcomes Scale (MOS) (Self-report)

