5.2 Sample size

Dose escalation on this study will be using EWOC design. There will be 3 patients per dose escalation and enrollment will be done sequentially. A **fixed sample size of 24 will be used.**

If a patient is not able to complete follow up to the toxicity assessment point of 4 months due to a toxicity judged not to be at least possibly related to therapy, then that patient will be replaced at the same dose level by the next patient enrolled into that cohort.

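### Neurocognition and quality of life are summarised only by a slope over time, which can hide or blunt an early decline

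*Combined protocol and SAP*

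**What the plan says.** Section 5.3.2.3 is the only analysis text for these outcomes: "Neurocognitive effect and QOL outcomes will be regressed over time using GEE model". The estimate to be reported is then named: "The population change over time (slope) will be estimated with 95%CI". Neither the form of the time term nor the working correlation is given. No visit-specific change, decline threshold, spline or categorical time term appears anywhere. Section 5.3.3 adds strata, not time points.

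Section 3.8.3 schedules the tests at baseline, at each follow-up for the first 7 months, and "then every 6 months thereafter (at 1, 4, 7, 13, 19, and 25 months". Appendix A agrees. Four of the seven assessments therefore fall within months 0 to 7.

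Section 2.2.4 calls the neurocognitive endpoint "Long-term neurocognitive outcomes". The quality-of-life endpoint in 2.2.5 carries no such qualifier, and neither outcome carries it in section 5.1.2. For progression, section 5.3.2.1 does plan a time-point estimate: "For a given time point, say 4 month, the rate of local/distant progression will be calculated with 95%CI". Section 5.2 states that a "fixed sample size of 24 will be used".

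**The concern.** A straight line in time cannot represent a fall after treatment followed by recovery or a plateau. When scores drop soon after baseline, part of the loss goes into the fitted intercept, which the plan does not report. When they later recover, the later visits pull the slope upward. A reader of these two secondary endpoints could be shown no change, or an improvement, when mean scores were lower at 1 and 4 months.

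The early visits are where such a loss would show and where most patients will still be under assessment. The background also gives avoidance of neurocognitive decline as a reason for focal radiation, so the early course matters to readers. The MTD, the DLT definition and the dose assignments do not use these instruments.

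**Working it through.** The plan gives no effect size, SD, expected slope or power for these outcomes, so it has no figure to reproduce. The check fits a straight line to assumed mean courses.

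**Inputs.** Visit times t = 0, 1, 4, 7, 13, 19, 25 months (section 3.8.3 and Appendix A). n = 24 (section 5.2). For attrition, section 1.0 reports one series "with a median survival from treatment of 7.5 months"; using it here is an assumption. The shapes, the loss d and the correlations are also assumptions.

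**Formula.** Slope b = Σw(t − t̄)y / Σw(t − t̄)², where t̄ is the w-weighted mean time. With full follow-up w = 1, and b equals the GEE slope under independence or exchangeable correlation. With attrition w = 0.5^(t/7.5), under independence. Expected patients are 24w: about 22, 17, 13, 7, 4 and 2 at months 1, 4, 7, 13, 19 and 25.

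**Worked case: loss d at months 1 and 4, recovered by 7.**
- Full follow-up: t̄ = 69/7 = 9.857 and Σ(t − t̄)² = 540.86. The numerator is (8.857 + 5.857)d = 14.714d, so b = +0.0272d per month, and 25b = +0.68d.
- The fitted intercept is −0.286d − 0.0272d × 9.857 = −0.55d. More than half of the loss sits there, unreported. The fitted change from month 0 to 4 is 4 × 0.0272d = +0.11d; the true change is −d.
- Attrition: t̄ = 4.599 and Σw(t − t̄)² = 134.57. The numerator is (0.912 × 3.599 + 0.691 × 0.599)d = 3.696d, so b = +0.0275d and 25b = +0.69d.

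**All shapes (slope × 25 months):**

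| Assumed course | Full follow-up | Attrition |
|---|---|---|
| Loss at 1 and 4, recovered by 7 | +0.68d | +0.69d |
| Loss at 1, 4 and 7, recovered by 13 | +0.81d | +0.45d |
| Loss at 1 and 4, straight-line recovery to 25 | +0.59d | +0.09d |
| Loss at 1 and 4, then half recovery | +0.11d | −0.08d |
| Loss at 4 and 7, recovered by 13 | +0.40d | −0.16d |
| Loss first at 4, straight-line recovery to 25 | +0.18d | −0.52d |
| Permanent loss from month 1 (true −1d) | −0.46d | −0.85d |
| Permanent loss from month 4 (true −1d) | −0.87d | −1.46d |

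A steady linear decline to −d at month 25 is recovered correctly, at −1.00d.

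**Simulation.** 1,000 runs per case, n = 24, score SD 1, d = 0.8 SD, within-patient correlation 0.6, exchangeable GEE with robust SE, CI = estimate ± 1.96 SE. Attrition is exponential with a 7.5-month median and independent of the scores. Entries are the share of runs with the 95% CI wholly below zero, full follow-up / attrition:

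| Assumed course | Slope | 4-month change |
|---|---|---|
| Loss at 1 and 4, recovered by 7 | 0% / 0.1% | 99% / 96% |
| Loss at 1 and 4, then half recovery | 1% / 9% | 99% / 96% |
| Permanent loss from month 1 | 77% / 59% | 99.6% / 96% |
| Steady linear decline of d over 25 months | 100% / 75% | 13% / 12% |

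In the first row the slope's CI lies wholly above zero in 97% / 46% of runs. Under attrition and correlation 0.4 to 0.8 that figure is 35–66%, and the 4-month CI lies below zero in 89–100%. With no true change, the slope CI excludes zero in 4–6% of runs per tail and the 4-month CI lies below zero in 2–4% (nominal 2.5%), so the slope intervals are slightly too narrow at this sample size.

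**The case against.** The strongest reply is that the slope matches the named endpoint. A dip that has gone by month 7 is not a long-term neurocognitive outcome, and for a steady decline the slope is far more sensitive than the 4-month change. This stands for neurocognition and is the reason to keep the slope. It does not cover quality of life, and it does not rescue the half-recovery case, where a lasting loss of d/2 is almost invisible to the slope.

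Second, the shapes and the 0.8 SD loss are assumed, and the sharpest contrast comes from a favourable scenario. Under attrition only two of the six recovery shapes give a clearly positive slope; one is near zero and three are negative. With smaller losses the added estimate also misses more: for the dip recovered by month 7, under attrition (200 runs per case), the 4-month CI lies below zero in about 36% of runs at d = 0.3 SD and about 70% at d = 0.5 SD. All of this stands. It limits how strongly the point can be put, but the protocol gives no expected course that would justify relying on a straight line alone.

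Third, precision will be lower than the simulation suggests. Section 3.8.3 makes baseline testing conditional on consent, section 4.6 takes patients off study at whole-brain radiotherapy, and real dropout may depend on the scores. If only 16 patients had baseline scores (an assumption), the 4-month half-width under attrition would rise from 0.40 to about 0.47 SD.

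Fourth, CNS toxicity is graded weekly during treatment and at 1 and 4 months (section 3.8.1). That covers clinical neurologic harm but does not summarise mean test scores. The comparison with section 5.3.2.1 is only suggestive, since that rate is for a time-to-event outcome.

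**Conclusion.** The concern holds. Followed as written, section 5.3.2.3 can report no change or an improvement when scores fell at months 1 and 4. The effect depends on the course: a dip with full recovery by month 7 is reversed in sign (about +0.7d over 25 months), a partly recovered loss is nearly invisible, a permanent loss keeps its sign with its size misstated (−0.46d to −1.46d against −1d), and a linear decline is captured correctly. That the slope is linear and runs to 25 months is inferred from the reporting of one slope and from the visit schedule; section 5.3.2.3 states neither. The sizes rest on assumed shapes, loss, correlation and score-independent attrition. These are secondary endpoints in a 24-patient phase I study and no dose decision depends on them. The change is worth making because it is cheap, but it is not critical.

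**What to change.** In section 5.3.2.3, keep the slope as the long-term summary. Add that the same GEE will be fitted with visit as a categorical factor, and that mean change from baseline with 95% CI will be reported for each instrument at 1, 4 and 7 months. Present later visits descriptively. Give the number of patients assessed at every visit, including baseline. Name one score per instrument in advance, because HVLT-R and FACT-Br each yield several.

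The cost is one sentence in the plan and a few lines of code, on data already scheduled. Four instruments at three visits give 4 × 3 = 12 intervals, and more if subscales are reported; they should be read as descriptive, without multiplicity adjustment. Each is wide: the 4-month half-width is about 0.35 SD with full follow-up and 0.40 SD with attrition (0.28 to 0.48 SD for correlation 0.8 to 0.4). Neither summary replaces the other.
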